#### 9.5.2.1 Duration of Response

DOR (for PR/CR and CR) is defined as the time from first observation of response (PR+CR/Marrow CR or CR/Marrow CR) to disease progression/relapse or death from any cause, whichever occurs first. Durations will be assessed in the ITT population with a PR or CR and calculated separately for subjects with CR/Marrow CR and those with PR+CR/Marrow CR combined. For subjects with a remission without subsequent disease progression/relapse or death on study, DOR will be censored at the time of the last disease assessment demonstrating a lack of disease progression/relapse. Subjects who receive another antineoplastic therapy in the absence of documented progression will be censored at the time of receiving off-protocol therapy for malignancy, EXCEPT that subjects who receive stem cell transplant in remission will continue to be followed for progression. Subjects who do not have a subsequent response assessment after their first observation of response will be censored at that date (day 1).

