Subjects will be stratified by baseline ECOG performance score (0 vs 1 or 2) and IPSS risk category (Intermediate-2 vs High risk).

Sample Size Considerations

Phase 1 Portion (minimum of 6 subjects per cohort): Six subjects are adequate to appropriately assess the safety profiles and DLT rates of differing dose levels of vadastuximab talirine in combination with azacitidine. If the true incidence rate of DLT is 10%, the probability of considering a dose level tolerable (ie, ≤ 1 of 6 subjects experiences a DLT) will be 88.6%. If the true incidence rate of DLT is 50%, the probability of considering a dose level tolerable will be 10.9%.

Phase 2 Portion (106 subjects): A sample size of 106 subjects will provide 85% power to detect a treatment difference in ORR, assuming an ORR of 30% for azacitidine alone vs 55% for the combination of vadastuximab talirine with azacitidine, at a 2-sided 0.1 alpha level.

Analysis Methods

The primary efficacy endpoint of the study is ORR in the Phase 2 Portion, defined as the proportion of subjects who achieve any category of CR (CR and Marrow CR) or PR based on the 2006 IWG criteria for MDS. Subjects who receive other MDS therapies before a response has been observed will be considered non-responders. The ORR will be summarized by treatment group and the corresponding 90% confidence intervals will be calculated. The treatment difference in ORR will be tested using a Cochran-Mantel-Haenszel test.

Secondary efficacy endpoints include CR rate, HI rate, DOR, PFS, rate of transformation to AML, and OS. Treatment differences in the rate of CR, HI, and transformation to AML will be analyzed by the same method as for ORR. DOR, PFS, and OS will be estimated with the Kaplan-Meier method and tested with the stratified log-rank test.

The primary analysis of efficacy will be based on the intent-to-treat (ITT) analysis set, which includes all subjects who are randomized in the Phase 2 Portion of the study.

Descriptive summaries of subject disposition, demographics, disease characteristics, baseline and pharmacodynamics biomarkers, extent of exposure to study treatment, and safety will be provided. The relationship of vadastuximab talirine PK and relevant pharmacodynamic endpoints, safety, or efficacy may be explored; these analyses, if conducted, will be descriptive.

DATE AND VERSION: 13 April 2017, Version 03

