13.2 Sample Size Estimation

Phase 1 Portion (minimum of 6 subjects per cohort): Six subjects are adequate to appropriately assess the safety profiles and DLT rates of differing dose levels of vadastuximab talirine in combination with azacitidine. If the true incidence rate of DLT is 10%, the probability of considering a dose level tolerable (ie, ≤ 1 of 6 subjects experiences a DLT) will be 88.6%. If the true incidence rate of DLT is 50%, the probability of considering a dose level tolerable will be 10.9%.

Phase 2 Portion (106 subjects): A sample size of 106 subjects will provide 85% power to detect a treatment difference in ORR, assuming an ORR of 30% for azacitidine alone vs 55% for the combination of vadastuximab talirine with azacitidine, at a 2-sided 0.1 alpha level.

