13.6.4.2 Secondary Efficacy Endpoints

Time-to-event variables (DOR, PFS, and OS) will be summarized descriptively using the Kaplan-Meier estimate. Additional details will be provided in the SAP. Secondary endpoints will be assessed in the ITT population (except as indicated below).

CR Rate: Response (CR/Marrow CR, PR, ORR [CR/Marrow CR+PR], HI rate, stable disease [SD], and PD) will be summarized descriptively by treatment arm. CR rate will be summarized with 90% confidence intervals. Rate of transformation to AML will also be summarized.

DOR (for PR/CR and CR): DOR is defined as the time from first observation of response (PR+CR/Marrow CR or CR/Marrow CR) to disease progression/relapse or death from any cause, whichever occurs first. Durations will be assessed in the ITT population with a PR or CR and calculated separately for subjects with CR/Marrow CR and those with PR+CR/Marrow CR combined. For subjects with a remission without subsequent disease progression/relapse or death on study, DOR will be censored at the time of the last disease assessment demonstrating a lack of disease progression/relapse. Subjects who receive another anti-neoplastic therapy in the absence of documented progression will be censored at the time of receiving off-protocol therapy for

malignancy, EXCEPT that subjects who receive stem cell transplant in remission will continue to be followed for progression.

Progression-free Survival: PFS is defined as the time from first dose of study medication to first documentation of disease progression/relapse, or to death due to any cause, whichever occurs first. For subjects without disease progression/relapse or death on study, PFS will be censored at the time of the last on-study disease assessment demonstrating a lack of disease progression/relapse. If more than one date of progression is available, the earliest date will be used to determine PFS. Subjects who receive another anti-neoplastic therapy in the absence of documented progression will be censored at the time of receiving off-protocol therapy for malignancy, EXCEPT that subjects who receive stem cell transplant in remission will continue to be followed for progression.

Overall Survival: OS is defined as the time from first dose of study medication to death due to any cause. For subjects not known to have died at the end of the study, OS will be censored at the time the subject was last known to be alive (including follow-up data).

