### Secondary Objectives:

- To evaluate the safety of the combination of vadastuximab talirine and azacitidine (Phase 1 and Phase 2 Portions)
- To compare the CR rate between treatment arms (Phase 2 Portion)
- To compare the hematologic improvement (HI) rate between treatment arms (Phase 2 Portion)
- To compare the duration of response (DOR) between treatment arms (Phase 2 Portion)
- To compare progression-free survival (PFS) between treatment arms (Phase 2 Portion)
- To compare the rate of transformation to acute myeloid leukemia (AML) between treatment arms (Phase 2 Portion)

- To compare the overall survival (OS) between treatment arms (Phase 2 Portion)

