### 3.2 Sample Size Considerations

Phase 1 Portion (minimum of 6 subjects per cohort): Six subjects are adequate to appropriately assess the safety profiles and DLT rates of differing dose levels of vadastuximab talirine in combination with azacitidine. If the true incidence rate of DLT is 10%, the probability of considering a dose level tolerable (ie,  $\leq 1$  of 6 subjects experiences a DLT) will be 88.6%. If the true incidence rate of DLT is 50%, the probability of considering a dose level tolerable will be 10.9%.

With this type of study design, the exact number of subjects needed to complete the Phase I Portion is unknown because it depends on the number of cohorts required to reach MTD. Approximately 24 subjects are expected to participate in the Phase 1 portion of this trial, assuming 4 dose-escalation cohorts of 6 subjects.

Phase 2 Portion (106 subjects): A sample size of 106 subjects will provide 85% power to detect a treatment difference in ORR, assuming an ORR of 30% for azacitidine alone vs 55% for the combination vadastuximab talirine with azacitidine, at a 2-sided 0.1 alpha level.

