### 3.4 Randomization

During the Phase 2 Portion of the study, subjects will be randomized in a 1:1 manner to azacitidine with vadastuximab talirine and azacitidine with placebo. Randomization will be stratified by ECOG performance status (0 vs 1 or 2) and IPSS score (Intermediate-2 vs High risk).

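### Between-arm duration of response is a comparison of responders only, so it is not randomised and can be biased in either direction; the documents also disagree on whether it is tested

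*SAP*

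**What the plan says.** The SAP's secondary objectives include "To compare the duration of response (DOR) between treatment arms (Phase 2 Portion"; protocol 8.2 has the same objective.

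On the analysis set, protocol 13.6.4.2 states "Durations will be assessed in the ITT population with a PR or CR", and SAP 9.5.2.1 repeats it: "Durations will be assessed in the ITT population with a PR or CR and calculated separately for subjects with CR/Marrow CR". Time runs from first observed response to progression, relapse or death.

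On the method, the documents differ. The protocol Synopsis states "DOR, PFS, and OS will be estimated with the Kaplan-Meier method and tested with the stratified log-rank test". Protocol 13.6.4.2 and SAP 9.5.2 instead describe DOR, PFS and OS as summarised descriptively by Kaplan-Meier; the SAP adds medians and quartiles with 90% intervals and curves by arm. The SAP names no log-rank test. SAP 1.1, which lists departures from the protocol, does not say that the test was dropped.

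Response itself is the primary Phase 2 endpoint, with the sample size set by "assuming an ORR of 30% for azacitidine alone vs 55% for the combination".

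**The concern.** Membership of the DOR analysis is decided after randomisation, by the outcome that the drug is meant to change. Describing the subset as part of the ITT population does not restore the randomised groups. If the planned difference in response occurs, the two groups of responders differ in who is in them as well as in what they received, and a difference in DOR mixes the two. If the extra responders have shorter responses than those who would respond on azacitidine anyway, DOR looks worse on the combination although no response was shortened. If theirs are longer, DOR looks better although no response was lengthened.

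Neither document gives a DOR analysis over all randomised subjects, or a caution on reading the by-arm result. The conflict over the test matters because a p-value would give a non-randomised contrast the standing of a formal comparison.

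**Working it through.** **Inputs from the documents.** Sample size and power: "A sample size of 106 subjects will provide 85% power to detect a treatment difference in ORR" (SAP 3.2). Error rate: "at a 2-sided 0.1 alpha level" (SAP 3.2). Allocation: "subjects will be randomized in a 1:1 manner to azacitidine with vadastuximab talirine and azacitidine with placebo" (SAP 3.4), so 53 per arm. Response rates: 30% and 55%.

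**The plan's own figure.** With unpooled variance, z = 0.25 / √[(0.30×0.70 + 0.55×0.45)/53] = 0.25/0.0929 = 2.691. Power = Φ(2.691 − 1.645) = 85.2%, which reproduces the stated 85%. Pooled variance gives 83.9%.

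**Size of the DOR groups.** 53 × 0.30 = 15.9 and 53 × 0.55 = 29.15, so about 16 vs 29 responders.

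**Share without a counterpart.** If no azacitidine responder is lost on the combination, (0.55 − 0.30)/0.55 = 25/55 = 45%. If a further d percentage points respond on azacitidine but not on the combination, the share is (25 + d)/55, which is larger.

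**Effect on DOR when no response is changed.** Assumptions: exponential durations; median 12 months in both arms for the 30% who respond on either treatment; median m for the 25% who respond only on the combination; 24-month cut-off. The experimental-arm median t solves (0.30/0.55)·0.5^(t/12) + (0.25/0.55)·0.5^(t/m) = 0.5. Hazard ratios (experimental vs comparator) and rejection rates come from 4,000 simulated trials per row, using an unstratified log-rank test at two-sided 0.10. The nominal rate is 5% in each direction.

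| m (months) | Experimental median (comparator 12.0) | HR | Significant against the drug | Significant for the drug |
|---|---|---|---|---|
| 4 | 7.0 | 1.49 | 30.2% | 0.3% |
| 6 | 8.6 | 1.35 | 19.9% | 0.8% |
| 9 | 10.5 | 1.13 | 9.4% | 2.9% |
| 12 | 12.0 | 1.00 | 5.1% | 5.8% |
| 18 | 14.3 | 0.83 | 1.1% | 13.5% |

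With censoring spread uniformly over 6 to 30 months (1,500 trials), m = 6 gives HR 1.31, so about 1.3 under either scheme. If the drug truly lengthens response by 25% in those who would respond anyway, m = 6 still gives HR 1.19.

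**Time in response over all randomised subjects.** Let RM(m) = (m/ln 2)(1 − 0.5^(24/m)) be the mean duration truncated at 24 months, with non-responders at zero.
- Comparator: 0.30 × RM(12) = 0.30 × 12.98 = 3.9 months.
- Experimental, m = 6: 3.9 + 0.25 × 8.12 = 5.9 months.
- Experimental, m = 12: 0.55 × 12.98 = 7.1 months.
- Experimental, m = 18: 3.9 + 0.25 × 15.66 = 7.8 months.

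**What this measure can hide.** Suppose the drug cuts every responder's median from 12 to 8 months. Time in response is 0.55 × RM(8) = 0.55 × 10.10 = 5.6 months, still above 3.9. With a cut to 6 months it is 0.55 × 8.12 = 4.5 months, again above 3.9.

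These means start the 24 months at response. A window starting at randomisation would give smaller values, since the first scheduled response assessment is at the end of Cycle 2.

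**The case against.** The strongest reply is that the plan already treats DOR as descriptive. SAP 9.5.2, which governs the DOR subsection, and protocol 13.6.4.2 both say so, and no DOR test or hazard ratio appears in the SAP. This largely stands: the rejection rates above apply only if the Synopsis test is run. What remains is the unreconciled Synopsis sentence, its absence from SAP 1.1, and by-arm medians and curves presented under an objective to compare, with no caution.

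A reader might also infer that the method will make an effective drug look harmful. The documents do not support that. They give no DOR figures, so nothing shows that extra responders would have shorter responses; equal durations give no bias and longer ones favour the drug. Even at m = 4, about 70% of simulated trials show no significant result against the drug.

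A further tempting reading is that time in response is the correct answer to the DOR objective and should replace responder DOR. It is not. When the responses of those who would respond anyway are unchanged, it favours the drug for any m above zero, because the extra responders add time. It partly restates the ORR difference and, as shown above, can stay favourable while every response is shortened.

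Finally, DOR is one of six secondary endpoints and has no decision rule. ORR, PFS and OS are assessed in the ITT set and are not touched by this point.

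**Conclusion.** The point holds in a limited form. By-arm DOR is a contrast between groups selected by a post-randomisation outcome that is planned to differ, 30% vs 55%. Under the no-loss assumption, 45% of experimental-arm responders have no comparator counterpart. The contrast is not randomised, and the direction of bias is unknown: HR about 1.3, 1.0 or 0.83 for assumed extra-responder medians of 6, 12 or 18 months against a common 12, with no true change in duration. These sizes rest on assumed medians, exponential durations and the simulated censoring.

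Separately, the Synopsis test and the descriptive wording in protocol 13.6.4.2 and SAP 9.5.2 contradict each other, and SAP 1.1 does not record a change. The primary analysis and its sample size are unaffected. This is a worthwhile, inexpensive improvement to a secondary analysis.

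**What to change.** 1. Remove DOR from the log-rank sentence in the Synopsis, or record in SAP 1.1 that the DOR test is not done, so that responder DOR is descriptive with no between-arm test.
2. State in SAP 9.5.2.1 that by-arm DOR describes responders and is not a randomised comparison.
3. Add a supplementary ITT analysis of mean time in response over a fixed window, with the between-arm difference and 90% CI. Use one time origin for everyone (randomisation is available for all ITT subjects, whereas the plan's PFS starts at first dose), count non-responders as zero and handle censoring. One way is the area between the Kaplan-Meier curves for the first of response, progression or death, and for progression or death.
4. Set the window to the follow-up available. SAP 3.1.2 ends response assessment at new anticancer therapy, and SAP 9.5 continues data collection only until all subjects are off study treatment, so complete response status over 24 months is not assured.

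The cost is wording, a new derivation and one table; no visits, sample size or treatment change. The downside is that time in response combines response rate with durability and can mask a true shortening, so it must be reported beside the responder DOR summary.

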#### 9.5.2.2 Progression-Free Survival

PFS is defined as the time from first dose of study medication to first documentation of disease progression/relapse, or to death due to any cause, whichever occurs first. For subjects without disease progression/relapse or death on study, PFS will be censored at the time of the last on-study disease assessment demonstrating a lack of disease progression/relapse. If more than one date of progression is available, the earliest date will be used to determine PFS. Subjects who receive another antineoplastic therapy in the absence of documented progression will be censored at the time of receiving off-protocol therapy for malignancy, EXCEPT that subjects who receive stem cell transplant in remission will continue to be followed for progression. Subjects who do not have a post-baseline response assessment after will be censored at baseline (day 1).

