### 9.5.4 Methods for Handling Dropouts and Missing Data

With the exception of time-related endpoints, missing observations will generally be treated as missing at random and will not be imputed, unless otherwise noted.

For time-related endpoints, DOR and PFS will follow [Table 2](#) below:

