**Table 2: Kaplan-Meier Analysis Rules**

Situation	Date of Progression or Censoring	Outcome
No baseline and/or post-baseline disease assessment	Date of first dose	Censored
No documented progression	Date of last adequate response assessment (or Study Day 1 in the absence of a post-baseline response assessment)	Censored
PD documented during or between scheduled visits	Date of response assessment demonstrating PD	Event
New subsequent cancer therapy initiated prior to documented progression	Start date of new subsequent cancer therapy	Censored
Death before first PD assessment	Date of death	Event
Death between response assessment visits	Date of death	Event

For concomitant medication dates, see [Section 5](#) for imputation rules. For missing or partial start and stop adverse event dates, see [Appendix 4](#) for imputation rules.

Note that the actual value for date (not imputed) will be presented in all data listings and imputed dates will be used for derivations only.

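### SAP censoring rules for subjects with no (later) response assessment make no exception for death, against the PFS and DOR definitions and Table 2's own death rows

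*SAP*

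**What the plan says.** **PFS.** Protocol 13.6.4.2, SAP Section 5 and SAP 9.5.2.2 all count death from any cause as an event. All three limit censoring at the last disease assessment to subjects without progression, relapse or death. SAP 9.5.2.2 then adds: "Subjects who do not have a post-baseline response assessment after will be censored at baseline (day 1".

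**DOR.** SAP 9.5.2.1 runs DOR from first response "to disease progression/relapse or death from any cause, whichever occurs first". Its last sentence is: "Subjects who do not have a subsequent response assessment after their first observation of response will be censored at that date (day 1".

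**Table 2.** SAP 9.5.4 states: "For time-related endpoints, DOR and PFS will follow" Table 2. Four of its rows matter here:

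| Situation | Date used | Outcome |
|---|---|---|
| "No baseline and/or post-baseline disease assessment" | First dose | Censored |
| No documented progression | "Date of last adequate response assessment (or Study Day 1 in the absence of a post-baseline response assessment") | Censored |
| "Death before first PD assessment" | Death | Event |
| "Death between response assessment visits" | Death | Event |

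No text or footnote says which row wins when a subject fits two.

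**The concern.** A subject who dies before any post-baseline assessment fits the first or second row above (censored at day 1) and also the third (event at death). A responder who dies with no further assessment is censored at the response date by the closing DOR sentence, but is an event under the DOR definition and the fourth row. Two programmers could each follow the SAP and report different event counts.

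Under the literal censoring text, the subjects removed are removed because they died. That is informative censoring, and it favours the arm with more early deaths. For PFS, the closing sentence and the first row reach only deaths before any assessment. The second row, read literally, would also censor deaths between later assessments, since any subject who dies without progression has no documented progression.

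The outputs at stake are the secondary PFS and DOR results. The SAP summarizes them descriptively by Kaplan-Meier; the protocol synopsis also names a stratified log-rank test. The PFS landmarks in SAP 9.5.2 start at 3 months (3 × 30.4375 = 91 days), after the first scheduled assessment, so every one of them would carry the effect.

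**Working it through.** Neither document gives an event count or power for PFS or DOR, so there is no planned figure to reproduce. The Phase 2 total of 106 at 1:1 is used only to get 53 per arm.

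**1. The texts side by side, for a death before any assessment**

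| Source | Treatment of the death |
|---|---|
| PFS definition (protocol 13.6.4.2, SAP 5 and 9.5.2.2) | Event |
| General PFS censoring sentence | Does not apply (limited to subjects without death) |
| Last sentence of SAP 9.5.2.2 | Censored, day 1 |
| Table 2, missing-assessment row | Censored, first dose |
| Table 2, no-progression row, fallback date | Censored, Study Day 1 |
| Table 2, death before first PD assessment | Event |

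The day-1 rules do not appear in protocol 13.6.4.2, to which protocol 13.6.1 refers for censoring, and SAP 1.1 does not list them as a change from protocol.

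**2. Window.** The first scheduled assessment is Cycle 2 Day 22-29: 28 + 22 = 50 to 28 + 29 = 57, so study Day 50-57 without delays.

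**3. Share dying in the window, d.** The documents do not give it. Assume exponential survival at the median OS in protocol 7.3 (21 to 24 months): d = 1 − 2^(−(day/30.4375)/median).

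| Median OS | Day 50 | Day 57 |
|---|---|---|
| 24 months | 0.0463 | 0.0526 |
| 21 months | 0.0528 | 0.0599 |

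Per arm this is 53 × 0.0463 = 2.5 to 53 × 0.0599 = 3.2 deaths.

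**4. Effect on the Kaplan-Meier estimate.** Censoring these deaths at day 1 removes them from both events and risk set, so PFS after the window is multiplied by 1/(1 − d). Check with 53 subjects and 16 events by 6 months, 3 of them early deaths:
- deaths as events: 37/53 = 0.698;
- the 3 deaths censored at day 1: 37/50 = 0.740;
- ratio: 0.740/0.698 = 1.06 = 1/(1 − 3/53).

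For an assumed true 6-month PFS of 70%: 0.70/(1 − 0.0463) = 0.734 and 0.70/(1 − 0.0599) = 0.745, a shift of 3.4 to 4.5 points.

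**5. Scale.** SE = √(0.7 × 0.3/53) = 0.0629. The 90% half-width is 1.645 × 0.0629 = 0.1035. The largest shift is (0.745 − 0.70)/0.0629 = 0.71 SE.

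**6. Between arms.** Equal d gives little bias in the difference. Suppose one arm has k early deaths and the other none, with 70% in both (assumed):

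| k | 0.70/(1 − k/53) | Shift toward the arm with the deaths |
|---|---|---|
| 1 | 0.7135 | 1.35 points |
| 2 | 0.7275 | 2.75 points |
| 3 | 0.7420 | 4.20 points |

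**7. Not sized.** Steps 3 to 6 cover only deaths before the first assessment, not the later deaths that a literal no-progression row would also censor. DOR is not sized either, because the documents give no death rate in responders.

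**The case against.** The strongest reply is that the SAP already resolves this. The general censoring sentences are limited to subjects without progression, relapse or death, and the closing sentences read naturally as the fallback date for that same group. SAP 9.5.4 points to Table 2, which has two explicit death rows. A fully literal reading of the no-progression row would censor every death without progression and leave the death rows with nothing to do. The PFS sentence also has a stray word in it, so a strict parse is on weak ground. This is probably what the authors meant, and under it the numerical effect is zero.

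It remains an inference. The preceding sentence carries its own qualifiers (no documented progression, and the transplant exception), while the closing sentence has none. The table offered as the tie-breaker contains the same conflict.

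Three further points stand, and they limit the size:
- PFS and DOR are secondary and summarized descriptively in the SAP.
- The 30- and 60-day mortality rates, reported by treatment group with 90% CIs, would show an early-death imbalance over nearly the same window.
- The figures rest on assumed survival and PFS rates. Eligibility requires a life expectancy of at least 12 weeks, and unscheduled Day 28-42 marrows would give some subjects an earlier assessment. Both lower d.

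A subject who starts new therapy and later dies also fits two Table 2 rows. That is a separate question, which the fix below does not settle.

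**Conclusion.** The concern holds. As written, the closing sentences of SAP 9.5.2.1 and 9.5.2.2 and the first two rows of Table 2 censor subjects whose deaths the definitions and the death rows count as events, and no precedence is stated. It should be fixed.

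The effect is zero if the death rows are applied. Under the literal censoring text, the range for deaths before the first assessment is about 0 to 4.5 points of 6-month PFS per arm. The upper end assumes exponential survival at a 21-month median OS, no assessment before Day 57 and a true PFS of 70%. Bias in the treatment comparison needs an imbalance in early deaths, which the documents do not allow one to predict. ORR, OS and the 30- and 60-day mortality rates do not change. Confidence is high that the texts conflict; whether the literal rule would be programmed is not known.

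**What to change.** Add *and who are not known to have died* in four places: the last sentence of SAP 9.5.2.1, the last sentence of SAP 9.5.2.2, and the first two rows of Table 2 (missing assessment and no documented progression). Under Table 2, state that the death and documented-progression rows take precedence over the missing-assessment rows.

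The cost is one short clause in two sentences and two table rows, plus one note. No new data and no protocol change are needed, and the edit brings the SAP into line with the protocol's definitions. SAP 1.0 provides for amendments of this kind before database lock.
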